### 7.14. End of study

End of study will be defined as when the project has recruited all patients successfully, the last patient has completed follow-up and all adverse events have been resolved.

### 7.15. Interventions

ECBx is a technique that has been developed at RSFT for the safe and effective retrieval of EC for research. The procedure involves cannulating a peripheral arm vessel and gently passing a metal guide wire in to collect EC. The procedure is very low risk and very well tolerated in patients. AE data from our pilot study support this statement. Of the 16 patients who received an ECBx, only 4 experienced minor bruising. All bruises resolved within a week of the procedure, did not require any additional treatment nor extend hospitalisation. No evidence of phlebitis or infection at the site of cannulation noted. More importantly the procedure did not restrict vascular access for standard of care.

#### Participants in Part 1 will receive only 1 biopsy.

#### Participants in Part 2 will receive up to 3 biopsies.

Some patients may also receive arterial lines and central lines as part of their standard of care. These wires will be collected if available and used for *in vitro* modelling.

A paired blood sample will be collected at the same time as the ECBx to look for biochemical markers of endothelial dysfunction, micro particles, Leukocyte function and circulating RNA. Serum and Plasma will also be collected and used to recreate the *in Vivo* phenotype, *In Vitro*.

Participants in Part 1 will have 1 blood samples of 25 ml collected from a line or venepuncture at the same time as the ECBx.

Participants in Part 2 will have 3 blood samples of 25 ml each collected from a line or venepuncture at the same time as the ECBx.

Tissue samples, blood for leukocyte analysis, and serum and plamsa for *in Vivo* phenotyping will be sent to [name] at the University of Surrey, where they will be prepared in room 35AY04 and then stored at -80°C in 37AY04.

Serum for microparticle analysis and circulating RNA will be sent to University of Cologne Germany and covered in a separate MTA.

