## 3. Protocol Summary

Title	Characterization of endothelial cells in multiple inflammatory pathologies			
Short title	JEDI-2			
Sponsor	Royal Surrey NHS Foundation Trust			
Design	Prospective observational study of three cohorts: i) healthy volunteers, ii) surgical patients, iii) critically ill patients.			
Primary objectives	To identify the changes in mRNA expression in endothelial cells from surgical patients and sepsis patients			
Secondary objectives	Stratification of patients based on mRNA expression from endothelial cells.			
	Characterisation of microparticles, histones and cell free DNA.			
Target accrual	Part 1: 25 healthy volunteers, 20 patients with sepsis and 20 elective abdominal surgery			
	Part 2: 20 patients with sepsis and 20 elective abdominal surgery			
Inclusion criteria (both parts)	
 
≥18 Years old
 
At RSFT for either and emergency admission to ICU, an elective surgery or as a healthy volunteer.
 
			
Exclusion criteria (both parts)	
 
Prisoners
 
Anticipated prohibitively difficult venous cannulation
 
Presenting with inflammatory diseases and disorders including but not limited to arthritis, peripheral artery disease, vasculitis, diabetes with end organ damage, cardiovascular disease and CKD.
 
Currently prescribed immunomodulatory medication or immunocompromised
 
Received chemotherapy within 2 weeks of predicted sampling.
 
History of recent trauma
 
			
Number of sites	1			
Duration of recruitment	12-18 months			
Duration of patient follow-up	Up to 28 days			
Definition of end of trial	End of follow-up of last patient			

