**Biomarkers of EC function**. It is not possible to directly measure the functions of the endothelium in patients but there are methods to gain insights. i) circulating levels of proteins reflect some aspects of EC function such as von Willebrand factor(13), Angiopoietin2(14) and angiotensin 2(15) ii) changes in circulating leukocytes (leukocytosis or leukopenia)(16) iii) micro particles released from EC can have pro-inflammatory, pro-thrombotic and vasoregulatory properties and also contain microRNAs (miRNAs), non-coding RNA molecules regulating genes (17,18) iv) circulating miRNA (19) V) measuring aspects of EC structure and function, including flow cytometry.

**RNA sequencing of EC.** We will process our patient-sourced ECs to preserve the mRNA for subsequent analysis. These analyses will provide insight into the EC function at the time of acquisition. RNA sequencing provides very detailed information about the relative abundance of many different transcripts. We can use knowledge of which transcripts are involved in which molecular pathways (for example a pro-inflammatory pathway like NF $\kappa$ B) to understand how putative pathways are expressed. Comparison of pathway expression between times within patient cohorts and between patient cohorts will allow us to see how EC respond in patients related to their clinical status.

**Hospital.** The Royal Surrey hospital intensive care unit (ICU) receives >600 patients per year who have had major surgery that typically has been prolonged (>6 hours) and often associated with major tissue injury and blood loss (~1L). These patients have systemic inflammation and the predominant feature of altered EC function is loss of vasomotor tone causing hypotension. This is a major reason why they are managed on the ICU where we have specific expertise in treating hypotension. As an acute hospital we also regularly treat patients with severe infections and admit >300 patients/y with sepsis to the ICU. These patients will invariably have features of systemic inflammation and altered EC function.

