#### 10. Statistics and data analysis

#### 10.1. Part 1 Sample size calculation

Power analysis using simulations generated by the package ssizeRNA suggests that a sample size of 16 can detect a fold change of 2 with power 0.8 when 20,000 genes are tested at a false discovery rate of 0.05 if the proportion of non-differentially expressed genes is 90%, the average number of reads mapped per gene is 10 and dispersion 0.1. For part 1 we will recruit 20 patients per cohort to ensure that we get enough useable mRNA for further analysis. We will also recruit 25 healthy volunteers, 20 for analysis and 5 to validate the method.

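### Microparticles and circulating RNA are assigned to serum although plasma is drawn at the same time, so release during clotting in the tube can bias cohort comparisons, above all those with healthy volunteers.

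*Protocol*

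**What the plan says.** Protocol section 7.15 (Interventions) takes a blood sample with each endothelial biopsy, "to look for biochemical markers of endothelial dysfunction, micro particles, Leukocyte function and circulating RNA". It then assigns the specimens:

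- For two of these assays the specimen is fixed: "Serum for microparticle analysis and circulating RNA will be sent to University of Cologne Germany and covered in a separate MTA".
- Plasma is drawn too, for another use: "Serum and Plasma will also be collected and used to recreate the" in-vivo phenotype in vitro. That material goes to the University of Surrey.
- The 25 ml sample is "collected from a line or venepuncture at the same time as the ECBx", with no rule by cohort.

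Section 3 lists "Characterisation of microparticles, histones and cell free DNA" as a secondary objective, and the objectives for Part 1 and Part 2 repeat it. Circulating RNA is not in that line of section 3, but it is a stated purpose of the blood sample. Section 5 explains the interest: "micro particles released from EC can have pro-inflammatory, pro-thrombotic and vasoregulatory properties and also contain microRNAs".

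The protocol gives no clotting time, spin or platelet-removal step. Section 7.17 makes late processing a major deviation and section 13.3 does the same for delayed transfer to the laboratory, but neither sets a time limit.

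**The concern.** The target is what the endothelium releases in the patient. Serum exists only once the blood has clotted in the tube. Clotting activates platelets and leukocytes, which shed particles and RNA of their own. A serum assay therefore adds an in-tube component to the in-vivo one.

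If that component were the same for everyone, it would mainly add background. It need not be. It depends on platelet count, leukocyte count, anticoagulant exposure and clotting time. These can plausibly differ between volunteers, patients 24 hours after major surgery and septic patients on ICU admission, and in Part 2 between the serial samples of one patient. A difference between cohorts in what happens in the tube could then be read as a difference in endothelial activation, or could hide a real one.

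**Working it through.** The protocol states no sample size, power or effect size for microparticles or circulating RNA, so there is no figure to reproduce. The check has three steps.

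**1. Can the in-tube part be adjusted for?**

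| Information needed | Patients | Healthy volunteers |
|---|---|---|
| Platelet and leukocyte counts | Whole blood counts taken from records (7.16) | None planned: no clinical characterisation in the schedule (6.1), oral history only (7.11) |
| Anticoagulant exposure | Targeted and concomitant medications (7.16) | Oral history only (7.11) |
| Clotting and processing time | No limit set | No limit set |

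Footnote 2 to the volunteer schedule mentions medical records, whereas 7.11 rules them out for this cohort. On either reading, no count at the time of sampling is planned. The leukocyte work on the study blood is described as function or activity, not as a count. Adjustment is therefore partly possible between patient cohorts and over time within patients, but not against controls.

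**2. How would a difference in the tube show up?** (Assumed values.) Set the control serum total to 1, with a share *s* from clotting and 1 − *s* from the patient. Suppose that another cohort has half the in-tube release and the same in-vivo level.

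- Measured total: (1 − *s*) + *s*/2 = 1 − *s*/2, an apparent fall of *s*/2.
- In-vivo rise that would be exactly hidden: (*s*/2)/(1 − *s*).

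| *s* (assumed) | Apparent fall in total | In-vivo rise hidden |
|---|---|---|
| 0.2 | 0.10 | 0.10/0.80 = 12.5% |
| 0.5 | 0.25 | 0.25/0.50 = 50% |
| 0.8 | 0.40 | 0.40/0.20 = 200% |

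**3. What would it do to a test?** (Assumed shift.) Section 10.1 gives 20 per patient cohort ("For part 1 we will recruit 20 patients per cohort to ensure that we get enough useable mRNA for further analysis") and 20 analysed volunteers ("We will also recruit 25 healthy volunteers, 20 for analysis and 5 to validate the method"). Take no true in-vivo difference, an in-tube difference of *d* SD, two-sided alpha 0.05 and *n* = 20 per cohort:

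P(reject) = 1 − Φ(1.96 − *d*/√(2/*n*)) + Φ(−1.96 − *d*/√(2/*n*)), with √(2/20) = 0.316.

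| *d* (assumed) | Normal approximation | Exact t-test |
|---|---|---|
| 0 | 0.05 | 0.05 |
| 0.25 | 0.12 | 0.12 |
| 0.5 | 0.35 | 0.34 |
| 0.8 | 0.72 | 0.69 |
| 1.0 | 0.89 | 0.87 |

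For *d* = 0.5: 0.5/0.316 = 1.58 and 1 − Φ(0.38) ≈ 0.35. A larger sample does not help: the standard error shrinks while *d* stays, so a false finding becomes more likely.

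**The case against.** The strongest case on the other side has five parts.

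- **The transfer agreement is not shown.** It may fix handling, and the assay may count only particles with an endothelial marker. This stands in part. Such a marker would lessen the microparticle problem, but the protocol names none, and it would not help total circulating RNA. The protocol itself fixes serum.
- **Patients' counts and drugs are recorded.** This stands. A reader might infer that the bias can never be separated out afterwards. Section 7.16 does not support that for comparisons among patients. For volunteers nothing comparable is planned.
- **The stakes are limited.** This stands. The blood assays are descriptive and secondary, and no sample size rests on them. The drift over 48 hours concerns only Part 2, for which section 8 already requires an amendment confirming the sampling requirements.
- **Nothing in the documents sizes the effect.** This stands. A reader might take an apparent fall of 10% to 40% as the size of the bias. It is only *s*/2 for assumed shares of 20% to 80% and an assumed halving of release. It is also a share of the total serum level; the hidden in-vivo rise is a different quantity, 12.5% to 200% under the same assumptions.
- **Histones and cell-free DNA.** A reader might extend the point to these because section 3 lists them with microparticles. The serum sentence does not cover them and no section assigns them a specimen, so there is no stated choice to correct.

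That serum carries in-tube release follows from what serum is. None of these objections removes it.

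**Conclusion.** The point holds for microparticles and circulating RNA. The protocol assigns both to serum, sends the plasma elsewhere and sets no common handling. Comparisons between cohorts for a secondary objective can therefore be biased, in a direction that cannot be known in advance. The comparison with healthy volunteers is the most exposed, because no platelet or leukocyte count is planned for them. Comparisons among patients can be adjusted in part.

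The size is unknown. The figures above show what assumed shifts would do and are not estimates. The conclusion rests on two assumptions: that in-tube release is not negligible, and that it differs between cohorts. Both are plausible given the three populations, but neither is measured in the documents.

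A reader might also infer that the main result is at risk. It is not: the primary objective concerns mRNA from endothelial cells taken by guidewire, which does not depend on this specimen.

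**What to change.** In section 7.15:

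1. Assign anticoagulated, platelet-depleted plasma to the microparticle and circulating RNA assays.
2. State one tube type, one spin procedure and one maximum time from draw to processing, the same in all cohorts and in both parts.
3. Keep serum for the in-vitro work.
4. If the receiving laboratory's assay needs serum, send both, name plasma as the primary matrix, and fix one clotting time and one spin time for all cohorts. The paired samples would then show how far the two matrices differ in each cohort.

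The transfer agreement needs a matching line.

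The cost is small: an extra spin step, and a check that the existing 25 ml covers the plasma needed. That check cannot be skipped, because the protocol does not break the volume down by use.

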### 7.16. Clinical characterisation and severity of illness scoring

To assess severity of illness we will use qSOFA score and NEWS2. These assessments can be performed by looking at routinely collected information as part of standard of care and provide insight into how sick the patient currently is.

For clinical characterisation we will look at the patients' medical records. We will collect information on every aspect of their admission including but not limited to:

- Blood changes in blood biochemistry, whole blood counts, blood gasses, etc
- Diagnosis what the patient is initially diagnosed with and the change over the course of their admission
- Targeted therapies use of medications like noradrenalin to treat hypotension, inotropes to modulate heart contractions and antibiotics for infection
- Concomitant medications use of other medications that are not specifically given for the indication of sepsis or post-surgical hypotension.
- MDT support data from physiotherapy, dietetic and Speech and language therapy.

#### 7.17. Protocol deviations

Major deviations from this protocol include mishandling of EC biopsy sample or blood, late processing of sample or incorrect storage of samples. These will be documented in the patients CRF and these samples may be excluded from analysis.

Minor deviation from this protocol is any other deviation not listed above. This will be documented and use to describe any outliers to the data in the final analysis

### 8. Progression to part 2

Progression to part 2 will only take place after review of data and adverse events from part 1 has been completed. The focus of the review will be to assess the variability of the data collected from part 1. If the variability is as predicted or less, no changes to the protocol will be made. If the variability is greater than expected, then the power will be recalculated. Based on the updated sample size, we will then reassess requirement for the current predicted sampling for part 2.

Progression to part 2 will happen after an amendment to the protocol has been made confirming sample size requirement and sampling requirements.

### 9. Adverse events

All patients will be monitored in ICU as part of their routine clinical care pathway will potentially experience a range of serious events, including organ dysfunction and death. None of these events are plausibly related to the study and therefore they will not be reported. They will however, be recorded and included in the analysis of this study.

For healthy volunteers, any adverse event related or non-related to the procedure will be recorded as an AE. Healthy volunteers will be followed-up at 1-week post procedure to confirm any adverse events. Any adverse events outstanding at a week post procedure will be followed-up until resolution.

In those patients in whom we have undertaken EC samples using a guidewire in a peripheral vein, we will monitor for complications related to this procedure. Our collaborators (combined experience of >20 years using these techniques) do not report any serious adverse events related to the procedure. This is supported by the AE reporting from our pilot study, JEDI-1 (IRAS 310961). Nonetheless we will be vigilant specifically for: inflammation of the vein (phlebitis), thrombosis of the vein (thrombophlebitis), or infection around the vein or venous puncture site (cellulitis) for the 3 days following the procedure.

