**New method** – **EC biopsy (ECBx).** Researchers studying endothelial dysfunction in humans have access to a range of commercially available cells for in vitro studies, but there are substantial limitations to their use. Unprecedented insights could be gained from serial sampling of ECs from individuals with acute conditions. The first successful attempt to obtain ECs from patients was reported in 1999 by Feng et al (11). Their technique involved inserting a stainless-steel J-shaped guidewires into major vessels and collecting the tissue adherent to the guidewire. The technique has evolved into using other vascular implements such as endovascular coils and stents to study the effects of diverse diseases (10,12). Believing that ECs from patients would offer improved insights into the vascular alterations that take place during systemic inflammation, we performed a pilot study (IRAS 310961).

We assessed the feasibility of ECBx in a surgical and intensive care setting. Discarded guidewires used during arterial and central line placements were collected from both surgical (n=16) and intensive care (n=16) patients. We also collected an additional biopsy from a peripheral arm vein in surgical patients only. ECs were then isolated from the guidewires and analysed using flow cytometry for absolute cell counts. From arterial lines we recovered an average of 536; from central lines we recovered an average of 598; from peripheral cannulation we obtained 736. One sample had RNA isolated which yielded a total

of 105ng of material. We also assessed the tolerability of the ECBx through collection of adverse event (AE) data and a short questionnaire. There were no serious AEs related to ECBx, with only four patients (25%) of patients experiencing minor bruising which resolved without any complication. Patient feedback from the pilot study was overwhelmingly positive. All said that the biopsy was bearable and they could tolerate additional ECBx (mean of 3 additional biopsies).

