### 9.1. Reporting procedures

Adverse event data will be collected from the moment consent is signed until follow-up is completed. Adverse events will be reported twice a year to the study sponsor to demonstrate compliance with the regulatory guidelines.

SAEs will be reported within 24 hours of the study team being made aware. SAEs will be reported to the sponsor and chief investigator who will report to the regulatory bodies.

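### Section 9 declares serious ICU events unrelated and unreported in advance, contradicting 24-hour SAE reporting (9.1) and the case-by-case judgement that 7.13 needs

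*Protocol*

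**What the plan says.** Protocol section 9 opens with patients who are in ICU as part of routine care. It says they "will potentially experience a range of serious events, including organ dysfunction and death". It then continues: "None of these events are plausibly related to the study and therefore they will not be reported". The next sentence qualifies this: "They will however, be recorded and included in the analysis of this study".

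A later paragraph of section 9 deals with patients who have had a guidewire biopsy in a peripheral vein: "we will monitor for complications related to this procedure". It names three conditions for particular vigilance: phlebitis, thrombophlebitis and "infection around the vein or venous puncture site (cellulitis) for the 3 days following the procedure".

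Section 9.1 states: "SAEs will be reported within 24 hours of the study team being made aware". These reports go to the sponsor and chief investigator and on to the regulatory bodies. The section also provides for a twice-yearly adverse event report to the sponsor, and it collects adverse events from signed consent to the end of follow-up.

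Section 7.13 says the trial team will withdraw a patient who has had an SAE caused by the trial procedures, with the reason documented in the eCRF.

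Section 8 allows progression to Part 2 only after "review of data and adverse events from part 1 has been completed".

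**The concern.** Exempting the expected events of critical illness from expedited reporting can be reasonable. The difficulty is how section 9 does it. The exemption rests on a causality statement made for a whole class of events before any has occurred, and not on an assessment of the event at hand. Section 9.1 does not acknowledge the exemption, and section 7.13 depends on the judgement that section 9 has already made.

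Two things are at stake. The first is practical: site staff faced with a death or new organ dysfunction in ICU have two opposite instructions. The second is attribution. If the biopsy or the paired blood draw led to a serious systemic event, that event would probably present as organ dysfunction or death, which is the class set aside as unrelated. Part 2 raises the number of biopsies per patient from one to as many as three, and the review of Part 1 adverse events is the safety check before that step.

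**Working it through.** No figure in the protocol is at issue, so there is none to reproduce. The check sets the sections against one another for the same event.

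**Step 1. One event, four sections.** Take new organ dysfunction in a biopsied sepsis patient in ICU, ten days after the biopsy.

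| Section | What it implies for this event |
|---|---|
| 9 | Unrelated by prior statement; not reported; recorded and analysed |
| 9.1 | If serious, reported within 24 hours to sponsor and chief investigator, then to regulators; no condition on relatedness and no reference to an exempt class |
| 7.13 | Withdrawal if caused by trial procedures, so someone must decide whether it was |
| 8 | Part of the adverse events reviewed before Part 2, if the patient is in Part 1 |

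Sections 9 and 9.1 give opposite answers on reporting. Sections 9 and 7.13 differ on whether relatedness is still open. For a death the withdrawal question falls away, but the reporting conflict remains. Section 9 also does not say whether it exempts the event from the 24-hour report, the twice-yearly report or both.

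**Step 2. What the other safeguards cover.**

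- Recording: the event and its date are captured. Section 9 describes no relatedness assessment for it.
- Procedure monitoring: the general commitment is broad, but the named conditions are three local ones and the stated window is 3 days.
- Follow-up: section 7.12 sets it at 28 days (±2) after enrolment. If biopsy and enrolment fall on the same day, 28 − 3 = 25 days of adverse event collection lie beyond the named window.

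The uncovered part is therefore a serious event that is not one of the three local conditions, or that appears after day 3. Such an event is recorded, but nothing in section 9 prompts anyone to ask whether the biopsy contributed.

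**Step 3. Who is in scope.** Cohort sizes are from sections 10.1 and 10.2, and biopsies per participant from section 7.15.

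- Sepsis cohorts, where emergency ICU admission is an inclusion criterion (section 7.5): 20 + 20 = 40 patients; biopsies at most 20 × 1 + 20 × 3 = 80.
- Surgical cohorts: the same numbers, 40 patients and at most 80 biopsies, but in scope only while the patient is in ICU. Section 7.3 does not require ICU admission.
- Both together: at most 80 + 80 = 160 patient biopsies. The Part 2 share is a ceiling (up to three each) and awaits the amendment that section 8 requires.
- Healthy volunteers are unaffected: section 9 records any adverse event in them, related or not.

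**Step 4. Effect on the progression review.** Section 8 puts the main weight of the review on the variability of the data, but completed review of adverse events is also a stated condition. The review would see the ICU events. It might not see a judgement on whether any of them was linked to the biopsy.

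**The case against.** The best defence is that section 9 has a sensible structure. The first paragraph deals with background events of critical illness; a separate paragraph deals with the procedure. On that reading the sentence is a specific exemption from the general rule in 9.1, badly cross-referenced, and not a ruling that no serious event can ever come from the biopsy. Section 7.13 supports this, since it foresees procedure-related SAEs. The monitoring commitment is not confined to the three named conditions, and a systemic infection from the puncture site would begin as a local infection, which is named.

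Much of this stands, and it limits the point. It does not remove it. Section 9.1 still contains no exemption, and nothing says how an event is sorted into background or procedure-related when the two look alike.

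Four stronger readings are tempting, and the documents do not support them:

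- **That the Part 1 review could not detect harm.** The events are recorded and analysed, adverse event monitoring is scheduled at every patient visit, and 28-day survival is collected. What may be missing is attribution.
- **That all study patients fall under the exemption.** The opening sentence of section 9 has two main verbs and has probably lost a word; it may mean only those patients who are in ICU.
- **That the small pilot shows the biopsy to be risky or unproven in ICU patients.** Section 5 says of the peripheral biopsy: "We also collected an additional biopsy from a peripheral arm vein in surgical patients only". It reports no *related* serious events, which is not the same as no serious events. In any case, the precision of the pilot has no bearing on whether two reporting rules conflict.
- **That ICU patients are the group with least earlier experience.** Section 5 describes no pilot healthy volunteers at all, whereas ICU patients did contribute guidewires from line placements.

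**Conclusion.** The contradiction is in the current text. Section 9 exempts a class of serious events on a causality statement made in advance, section 9.1 admits no exemption, and section 7.13 needs a judgement on the individual event.

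The consequence is narrower than loss of safety data. A serious systemic or later consequence of the biopsy, presenting as organ dysfunction or death, may be neither attributed to the biopsy nor reported promptly, and the Part 1 review may lack that attribution. How often this would occur cannot be estimated from the protocol. The scope is the 40 sepsis patients, with at most 80 biopsies, and surgical patients while in ICU.

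The conclusion assumes that "None of these events are plausibly related to the study and therefore they will not be reported" refers to the serious ICU events of the sentence before it, and that relatedness for these events is not laid down in some other instruction to the site. This should be corrected, preferably while Part 1 is still collecting events, because those events feed the progression review.

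**What to change.** Reconcile sections 7.13, 9 and 9.1 so that one event leads to one instruction.

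1. Replace the blanket statement in section 9 with a list of expected events of critical illness.
2. Exempt a listed event from 24-hour reporting only once the investigator has recorded, for that event, that it is not related to the biopsy or blood sampling.
3. State in section 9.1 that all other SAEs, including any not yet assessed, follow the 24-hour rule, and refer to the list. Say whether exempt events enter the twice-yearly report.
4. Refer section 7.13 to the same recorded judgement, and supply it to the review in section 8.

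The cost is revised protocol wording, one relatedness field on the eCRF, and an investigator judgement on each serious event already being recorded. The last is the real burden. Section 10.3 says only patients who need organ support are transferred to ICU, so such events may be frequent. No extra visits, samples or participants are needed. Section 8 already requires an amendment before Part 2, but waiting for it would leave Part 1 events without the assessment.
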